10.3.4. Interim Analyses

An interim analysis may be conducted after approximately 24 subjects have completed the Day 42 FBF procedure, unless the blinded sample size re-estimation suggests a different sample size. If the interim analysis for this study is expected to occur after the interim analysis of the larger Phase III ASCEND program, then this interim analysis may occur sooner.

If the observed percent change between daprodustat and darbepoetin alfa for FBF ratio from Day 1 to Day 42 in response to acetylcholine is less than 8%, then the study will be stopped. Assuming a true percent change of 25% and a standard deviation of 0.272, the decision guideline was determined to have favorable operating characteristics, such as an unconditional power of <30%, and an acceptable low probability of false stop (<10%). Since the study will not be stopped for positive results, type I error will not be inflated. If the sample size changes based on the blinded sample size re-estimation, then the operating characteristics may be revised to reflect a different standard deviation. Any such changes will be documented in the RAP.

While the above is a guideline for stopping the trial due to futility, the totality of the data will be considered when making the decision at the time of the interim analysis.

Further details of the interim analysis will be included in the RAP.

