10.1. Sample Size Determination

A sufficient number of participants will be enrolled such that at least 50 participants comprise the Pharmacodynamic Per-Protocol (PDPP) Population (See Section 10.3.1). The sample size may be adjusted following the sample size re-estimation (See Section 10.1.2).

Based on a coefficient of variation of 0.277 of change from baseline FBF ratio, a sample size of 25 participants per treatment arm, provides 80% power to show a statistically significant difference between groups, assuming a true difference of at least 25% (Cheriyana, 2011) at the alpha = 5% level of significance.

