10.3.3. Other Analyses (Pharmacodynamic)

The primary analysis model will be based on the acetylcholine challenge agent data.

Following log-transformation the change in FBF ratio from Day 1 to Day 42 will be analyzed using analysis of covariance (ANCOVA) model including terms for the treatment group (daprodustat/darbepoetin alfa), challenge agent dose, treatment*challenge agent dose interaction term, FBF ratio on Day 1, gender, and site stratification variable. The primary comparison of interest is the difference between treatment groups in the primary endpoint associated with the acetylcholine challenge. The point estimate and corresponding 95% confidence interval will be derived, using the residual error from the model, for the comparison of the treatment groups. These estimates will be back-transformed to provide the point estimate and corresponding 95% confidence interval (CI) for the ratio of daprodustat/darbepoetin alfa for the primary analysis.

In addition, this model will provide the supporting analysis to the primary analysis deriving the estimates and 95% CIs for (1) Change in FBF ratio from Day 1 to Day 42 for each treatment group and (2) Difference in FBF ratio between the challenge agent and saline on both Day 1 and Day 42. These estimates will be back-transformed to provide the point estimates and corresponding 95% CIs for the ratios for “Day 42/Day 1” and “challenge agent/saline” (for each challenge agent dose level) where saline is considered as providing assay sensitivity for the challenge agent.

The first secondary endpoint will use the same model as the primary endpoint with absolute FBF instead of FBF ratio as the dependent variable. The other challenge agents, sodium nitroprusside and L-NMMA, will utilize a similar model. If an insufficient number of subjects in the PDPP population have complete Day 1 and Day 42 data for either of the two remaining challenge agents, then that particular challenge agent will not

be statistically analysed. Instead, a summary table and subject level listing will be generated.

The secondary endpoints evaluating the within treatment comparison of daprodustat and darbepoetin alfa will utilize an ANCOVA model including terms for challenge agent dose, FBF measurement on Day 1, gender, and site. This model will be run for both treatment groups for each of the three challenge agents and for FBF ratio and absolute FBF.

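### The unconditional power below 30% quoted for the futility rule does not fit the 25% effect and SD of 0.272 it is tied to: under those inputs it is about 78–79%

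*Protocol*

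**What the plan says.** Protocol section 10.3.4 provides for an optional futility look: "An interim analysis may be conducted after approximately 24 subjects have completed the Day 42 FBF procedure". If the observed daprodustat versus darbepoetin alfa difference in FBF ratio change "in response to acetylcholine is less than 8%, then the study will be stopped". The justification opens with "Assuming a true percent change of 25% and a standard deviation of 0.272" and calls the resulting characteristics favourable, "such as an unconditional power of <30%, and an acceptable low probability of false stop (<10"%). The section does not define unconditional power. It describes the rule as a guideline to be weighed with all the data, and leaves further detail to the RAP.

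Section 10.1 sizes the trial on the same effect and variability. Its variability input is worded as "Based on a coefficient of variation of 0.277 of change from baseline FBF ratio". From that input it concludes that "a sample size of 25 participants per treatment arm, provides 80% power" for a 25% difference at the 5% level. The table in section 10.1.1 gives 81% for the same case.

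The SAP (sections 2.1 and 3.1) records that the study was terminated and that no interim analysis will be done. It therefore never explains the term.

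**The concern.** In ordinary use, unconditional power is the probability, before any data are seen, that the trial ends in a significant result under a stated true effect. Under a true 25% change that is the design power, less whatever the futility rule costs. A value below 30% cannot be squared with the 80% in section 10.1. A low value can be favourable only if it describes the prospects of a trial at or near the stopping boundary, or of a treatment with a small true effect. In either case the 25% assumption is not the one that produces it, or not the only one.

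What is at stake is the accuracy of one of the two operating characteristics offered for the rule. A reader weighing a stop needs to know which effect the figure assumes. The answer moves from roughly 10% to roughly 80% depending on that choice.

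**Working it through.** **Inputs.** True change 25%, ln 1.25 = 0.2231 (10.3.4). Cut-off 8%, ln 1.08 = 0.0770 (10.3.4). SD 0.272 (10.3.4), which is the log-scale SD for the CV in 10.1: √ln(1 + 0.277²) = 0.2719. Log-scale analysis (10.3.3: "Following log-transformation the change in FBF ratio from Day 1 to Day 42 will be analyzed"). Final size 25 per arm (10.1). Allocation 1:1 (7.3).

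**Assumptions.** The approximately 24 completers are taken as 12 per arm, leaving 13 per arm. The test is two-sided at 5%, inferred from the alternative hypothesis in section 10. No precision is credited to covariates.

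**Standard errors.** SD × √(2/n):
- interim: 0.272 × √(2/12) = 0.1110
- final: 0.272 × √(2/25) = 0.0769
- second stage: 0.272 × √(2/13) = 0.1067

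**1. The plan's own figures.**
- Design power: 0.2231/0.0769 = 2.900. The noncentral t with 48 df gives 81.1%; the normal formula with z = 1.96 gives Φ(2.900 − 1.960) = 82.7%. The plan states 80% and 81%, so this reproduces.
- False stop: Φ((0.0770 − 0.2231)/0.1110) = Φ(−1.316) = 9.4%. The plan states below 10%, so this reproduces too.

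**2. Bound from the protocol alone.** Power with the rule cannot be less than power without it minus the probability of a false stop. That is more than 80% − 10% = 70%, whatever model is used.

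**3. Unconditional power with the rule, true change 25%.** This is P(interim estimate ≥ ln 1.08 and final test significant), bivariate normal with correlation √(12/25) = 0.693. It is 79.3% with the z critical value (1.960) and 78.2% with the t critical value (2.011). A simulation of one million trials with the z critical value gives 79.4%. The rule costs about 3 points: 82.7 − 79.3 = 3.3 before rounding.

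**4. Other readings that keep the 25% effect.**
- Conditional power at an observed 8%. With z, the final log difference must reach 1.960 × 0.0769 = 0.1508, so the second stage must average (25 × 0.1508 − 12 × 0.0770)/13 = 0.2189. Then 1 − Φ((0.2189 − 0.2231)/0.1067) = 51.6%. With t the result is 48.8%.
- Chance of final success had the trial continued, averaged over the stop region: with z, 0.0333/0.0940 = 35.4%; with t, 0.0310/0.0940 = 33.0%.

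**5. Readings that drop the 25% effect.**

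| Quantity | Result |
|---|---|
| Power at a true 8%, no rule | 16.5% (noncentral t), 16.9% (normal) |
| Power at a true 8%, with the rule (z) | 15.3% |
| Predictive power at an observed 8%, flat prior | 17.8% (z), 16.6% (t) |
| Conditional power at an observed 8%, current trend | 9.2% (z), 8.1% (t) |

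**6. What a value of 30% would need.** With the rule in place, unconditional power falls to 30% only if the true change is about 12%, or if the SD is about 0.54, twice the stated value.

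**7. Sensitivity to an earlier look**, which section 10.3.4 allows (z critical value):

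| Per arm at interim | False stop | Power with rule, true 25% | Conditional power at observed 8%, true 25% | Predictive power at observed 8% |
|---|---|---|---|---|
| 8 | 14.1% | 75.3% | 65.7% | 25.5% |
| 10 | 11.5% | 77.6% | 59.2% | 21.7% |
| 12 | 9.4% | 79.3% | 51.6% | 17.8% |

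An earlier look does not bring unconditional power near 30%. It does take false stop above the stated 10%.

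**The case against.** The strongest reply is that the 30% figure may be a correct number under an unclear name. The section calls it favourable, which makes sense only for the prospects of a trial at the boundary or of a treatment with a small true effect, and three such quantities do fall below 30%. This stands in part: the documents do not show that the sponsor miscalculated. They do show that the sentence as printed attaches the figure to an assumption under which it is false. Nor do they say which of the three quantities was meant, so none should be written in on the sponsor's behalf.

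A reader might infer that the 8% cut-off rests on a wrong figure and is unsound. The documents do not support that. The other stated support, the false-stop probability, reproduces under exactly the stated inputs, and the rule costs only about 3 points of power.

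A reader might also infer that decision-makers were told a result below 8% leaves under a 30% chance of success even if the 25% effect is true. Section 10.3.4 makes no statement about success given an observed result. The value near one half applies only at exactly 8%; across the stop region it is about one third. The rule is also a guideline read with the rest of the data.

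Finally, no decision now depends on the sentence. That is true and limits its importance, but the record still carries a wrong operating characteristic.

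**Conclusion.** The point holds as a mislabelled or wrongly paired figure. Under a true 25% change and SD 0.272, unconditional power is about 81% without the futility rule and 78–79% with it, against a stated value below 30%. The bound of more than 70% follows from the protocol's own 80% power and sub-10% false stop. The exact figures rest on 12 per arm at the interim, 25 per arm at the end, the log scale, a two-sided 5% test and no covariate gain; small differences within the ranges reflect t versus z critical values.

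No reading examined here that keeps the 25% effect falls below 30%. The finding goes no further than the stated figure: it does not discredit the threshold, and it has no bearing on any reported result.

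**What to change.** Rewrite the justifying sentence in section 10.3.4 in three parts:

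1. Under a true 25% change and SD 0.272, with 12 per arm at the interim, false stop is about 9.4% and unconditional power with the rule is about 78–79%.
2. Name and define the quantity meant by the 30% figure, with its own assumption stated separately from the 25% effect. The sponsor should say which quantity was computed.
3. Report that conditional power under the 25% effect, at an observed 8%, is about 50%, so that the boundary is described under the design assumption as well.

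The cost is one sentence in the protocol, or a clarifying note to file, plus a check of the sponsor's original calculation. Design, threshold and conduct do not change. Because the SAP cancels the interim, the benefit is an accurate record and a correct statement if the text is reused in another study.

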12. APPENDICES

12.1. Appendix 1: Abbreviations and Trademarks

ACh	Acetylcholine
AE	Adverse event
AESI	Adverse event of special interest
AI	Augmentation Index
ALT	Alanine transaminase
ANCOVA	Analysis of Covariance
AST	Aspartate transaminase
AUC	Area under curve
AV	Arteriovenous
BCRP	Breast cancer resistance protein
BP	Blood pressure
CI	Confidence interval
CIOMS	Council for International Organizations of Medical Sciences
CKD	Chronic kidney disease
CFR	Code of Federal Regulations
CL/F	Total body clearance
C _{max}	Maximum plasma concentration
CONSORT	Consolidated Standards of Reporting Trials
CPK	Creatine phosphokinase
CSR	Clinical Study Report
CV	Cardiovascular
CV _b	Between-subject coefficients of variation
CYP	Cytochrome P ₄₅₀
dL	Decilitre
ECG	Electrocardiogram
ECHO	Echocardiogram
eCRF	Electronic case report form
eGFR	Estimated glomerular filtration rate
EPI	Epidemiology
EPO	Erythropoietin
FBF	Forearm Blood Flow
FRP	Females of reproductive potential
FSH	Follicle stimulating hormone
g	Gram
GCP	Good Clinical Practice
GI	Gastrointestinal
GSK	GlaxoSmithKline
HbA _{1c}	Glycated hemoglobin
hCG	Human chorionic gonadotrophin
HD	Hemodialysis dependent
HDL-c	High density lipoprotein-C
Hgb	Hemoglobin

HIF	Hypoxia-inducible factor
HIPAA	Health Insurance Portability and Accountability Act
HPLC	High-performance liquid chromatography
HR	Heart rate
HRT	Hormone replacement therapy
hs-CRP	High sensitivity C-reactive protein
IB	Investigator's Brochure
ICF	Informed Consent Form
ICH	International Conference on Harmonization
IDMC	Independent Data Monitoring Committee
IEC	Independent Ethics Committee
IgM	Immunoglobulin M
INR	International Normalized Ratio
IRB	Institutional Review Board
IP	Investigational Product
IUD	Intrauterine device
IUS	Intrauterine hormone-releasing system
IV	Intravenous
IWRS	Interactive Web Response System
KDIGO	Kidney Disease: Improving Global Outcomes
Kg	Kilogram
L	Liter
LDH	Lactate dehydrogenase
LDL-C	Low density lipoprotein-C
L-NMMA	NG-monomethyl arginine acetate
LVEF	Left Ventricular Ejection Fraction
µg	Microgram
µmol	Micromole
MCH	Mean corpuscular hemoglobin
MCHC	Mean corpuscular hemoglobin concentration
MCV	Mean corpuscular volume
MedDRA	Medical Dictionary for Regulatory Activities
MI	Myocardial infarction
Mg	Milligram
mmHg	Millimeters of mercury
mL	Milliliter
MSDS	Material Safety Data Sheet
Msec	Millisecond
NC-OFPP	Non-Contact, Optical Forearm Plethysmography
ND	Not on dialysis
ng	Nanogram
nmol	Nanomole
NO	Nitric oxide
NSAID	Non Steroidal Anti Inflammatory Drug
NYHA	New York Heart Association
PAH	Pulmonary artery hypertension

PASP	Pulmonary artery systolic pressure
PCI	Percutaneous Coronary Intervention
PCM	Progressive cardiomyopathy
PD-PP	Pharmacodynamic Per-Protocol Population
PED	Peritoneal dialysis
PHD	Prolyl hydroxylase
PHI	Prolyl hydroxylase inhibitor
PK	Pharmacokinetic
PRVP	Peak Right Ventricular Pressure
PSRAE	Possible suicidality related adverse events
PWV	Pulse Wave Velocity
QC	Quality Control
QTcB	QT duration corrected for heart rate by Bazett's formula
RAP	Reporting and Analysis Plan
RBC	Red blood cell
RDW	Red blood cell distribution width
RNA	Ribonucleic Acid
rhEPO	Recombinant human erythropoietin
SAE	Serious adverse event
SC	Subcutaneous
SD	Standard deviation
SNP	Sodium nitroprusside
SoA	Schedule of Events
SRM	Study Reference Manual
SUSAR	Suspected Unexpected Serious Adverse Reactions
TSAT	Transferrin saturation
U	Units
ULN	Upper limit of normal
VEGF	Vascular Endothelial Growth Factor
WBC	White blood cell
WOCBP	Woman of Child Bearing Potential
UK	United Kingdom

Trademark Information

Trademarks of the GlaxoSmithKline group of companies
NONE

Trademarks not owned by the GlaxoSmithKline group of companies
Aranesp
HemoCue
MedDRA
RAMOS-NG
SphygmoCor

12.2. Appendix 2: Clinical Laboratory Tests

All study-required laboratory assessments will be performed by a central laboratory with the exception of HemoCue Hgb, INR measurements and urine pregnancy tests which will be performed at the clinical site. The results of each HemoCue Hgb must be entered into the participant's eCRF.

A local Hematology lab will be allowed in the event that central labs are unavailable.

Tests included in [Table 4](#) must be conducted in accordance with the Laboratory Manual and Study Protocol SoA (See [Section 2](#)). Laboratory requisition forms must be completed and samples must be clearly labeled with the participant number, protocol number, site/centre number, and visit date. Details for the preparation and shipment of samples will be provided by the laboratory and are detailed in the SRM. Reference ranges for all safety parameters will be provided to the site by the laboratory responsible for the assessments.

Refer to the SRM for appropriate processing and handling of samples.

Table 4 Protocol Required Laboratory Assessments

Laboratory Assessments	Parameters		
Hematology	Platelet count	RBC indices:	WBC count with Differential
	RBC count	MCV	Neutrophils
	Reticulocyte count	MCH	Lymphocytes
	Hgb	MCHC	Monocytes
	Hematocrit	RDW	Eosinophils
	WBC count (Absolute)		Basophils
Clinical Chemistry¹	Sodium (serum)	AST ¹	Carbon Dioxide (total)
	Potassium (serum)	ALT ¹	Albumin
	Creatinine (serum)	Chloride (serum)	Urea (serum)
	Glucose	Bilirubin (total and direct/indirect)	Alkaline Phosphatase
Other laboratory tests	Serum ferritin	TSAT	hs-CRP
	Total cholesterol	LDL-C (direct)	HDL-C
	Triglycerides	Serum/Urine hCG pregnancy test ²	FSH ³
	HbA1c	Folate	Vitamin B ₁₂
	Serology (hepatitis B surface antigen [HBsAg], and hepatitis C virus antibody)		

Abbreviations: RBC: red blood cells, WBC, white blood cells; MCV, mean corpuscular volume; MCH, mean corpuscular hemoglobin; MCHC, mean corpuscular hemoglobin concentration; RDW, red blood cell distribution width, AST, aspartate transaminase; LDL-C, low density lipoprotein-C; HDL-C, high density lipoprotein-C, hCG= human chorionic gonadotropin.

¹Details of Liver Chemistry Stopping Criteria and Required Actions and Follow-Up Assessments after liver stopping or monitoring event are given in Section 8.1.1 and Section 12.6.

²For females of reproductive potential only.

³Screening only. As needed in postmenopausal women where their menopausal status is in doubt (see Inclusion Criteria Section 6.1).

All laboratory tests with values that are considered clinically-significantly abnormal during participation in the study or within 14 (± 3) days after the last dose of study treatment should be repeated until the values return to normal or baseline. If such values do not return to normal within a period judged reasonable by the investigator the sponsor should be notified.

12.3. Appendix 3: Study Governance Considerations

Regulatory and Ethical Considerations

- This study will be conducted in accordance with the protocol and with:
 - Consensus ethical principles derived from international guidelines including the Declaration of Helsinki and Council for International Organizations of Medical Sciences (CIOMS) International Ethical Guidelines
 - Applicable ICH Good Clinical Practice (GCP) Guidelines
 - Applicable laws and regulations
- The protocol, protocol amendments, ICF, Investigator Brochure, and other relevant documents (e.g., advertisements) must be submitted to an IRB/IEC by the investigator and reviewed and approved by the IRB/IEC before the study is initiated.
- Any amendments to the protocol will require IEC/IRB approval before implementation of changes made to the study design, except for changes necessary to eliminate an immediate hazard to study participants.
- The investigator will be responsible for the following:
 - Providing written summaries of the status of the study to the IRB/IEC annually or more frequently in accordance with the requirements, policies, and procedures established by the IRB/EC
 - Notifying the IRB/IEC of SAE or other significant safety findings as required by IRB/IEC procedures
 - Providing oversight of the conduct of the study at the site and adherence to requirements of 21 CFR, ICH guidelines, the IRB/IEC, European regulation 536/2014 for clinical studies (if applicable), and all other applicable local regulations

Financial Disclosure

Investigators and sub-investigators will provide the sponsor with sufficient, accurate financial information as requested to allow the sponsor to submit complete and accurate financial certification or disclosure statements to the appropriate regulatory authorities. Investigators are responsible for providing information on financial interests during the course of the study and for 1 year after completion of the study.

Informed Consent Process

- The investigator or his/her representative will explain the nature of the study to the participant or his/her legally authorized representative and answer all questions regarding the study.
- Participants must be informed that their participation is voluntary. Participants or their legally authorized representative will be required to sign a statement of

informed consent that meets the requirements of 21 CFR 50, local regulations, ICH guidelines, Health Insurance Portability and Accountability Act (HIPAA) requirements, where applicable, and the IRB/IEC or study center.

- The medical record must include a statement that written informed consent was obtained before the participant was enrolled in the study and the date the written consent was obtained. The authorized person obtaining the informed consent must also sign the ICF.
- Participants must be re-consented to the most current version of the ICF(s) during their participation in the study.
- A copy of the ICF(s) must be provided to the participant or the participant's legally authorized representative.
- Participants who are rescreened are required to sign a new ICF.

The ICF may contain a separate section that addresses the use of remaining mandatory samples for optional exploratory research in accordance with SOP-GSKF-410. The investigator or authorized designee will explain to each participant the objectives of the exploratory research. Participants will be told that they are free to refuse to participate and may withdraw their consent at any time and for any reason during the storage period. A separate signature will be required to document a participant's agreement to allow any remaining specimens to be used for exploratory research. Participants who decline to participate will not provide this separate signature.

Data Protection

- Participants will be assigned a unique identifier by the sponsor. Any participant records or datasets that are transferred to the sponsor will contain the identifier only; participant names or any information which would make the participant identifiable will not be transferred.
- The participant must be informed that his/her personal study-related data will be used by the sponsor in accordance with local data protection law. The level of disclosure must also be explained to the participant.
- The participant must be informed that his/her medical records may be examined by Clinical Quality Assurance auditors or other authorized personnel appointed by the sponsor, by appropriate IRB/IEC members, and by inspectors from regulatory authorities.

Publication Policy

- The results of this study may be published or presented at scientific meetings. If this is foreseen, the investigator agrees to submit all manuscripts or abstracts to the sponsor before submission. This allows the sponsor to protect proprietary information and to provide comments.
- The sponsor will comply with the requirements for publication of study results. In accordance with standard editorial and ethical practice, the sponsor will generally support publication of multicenter studies only in their entirety and not

as individual site data. In this case, a coordinating investigator will be designated by mutual agreement.

- Authorship will be determined by mutual agreement and in line with International Committee of Medical Journal Editors authorship requirements.

Dissemination of Clinical Study Data

Study information from this protocol will be posted on publicly available clinical trial registers before enrollment of participants begins.

Where required by applicable regulatory requirements, an investigator signatory will be identified for the approval of the clinical study report. The investigator will be provided reasonable access to statistical tables, figures, and relevant reports and will have the opportunity to review the complete study results at a GSK site or other mutually agreeable location.

GSK will also provide the investigator with the full summary of the study results. The investigator is encouraged to share the summary results with the study participants, as appropriate.

GSK will provide the investigator with the randomization codes for their site only after completion of the full statistical analysis.

The procedures and timing for public disclosure of the results summary and for development of a manuscript for publication will be in accordance with GSK Policy.

A manuscript will be progressed for publication in the scientific literature if the results provide important scientific or medical knowledge.

Data Quality Assurance

- All participant data relating to the study will be recorded on printed or electronic CRF unless transmitted to the sponsor or designee electronically (eg, laboratory data). The investigator is responsible for verifying that data entries are accurate and correct by physically or electronically signing the CRF.
- The investigator must maintain accurate documentation (source data) that supports the information entered in the CRF.
- The investigator must permit study-related monitoring, audits, IRB/IEC review, and regulatory agency inspections and provide direct access to source data documents.
- The sponsor or designee is responsible for the data management of this study including quality checking of the data.
- Study monitors will perform ongoing source data verification to confirm that data entered into the CRF by authorized site personnel are accurate, complete, and verifiable from source documents; that the safety and rights of participants are being protected; and that the study is being conducted in accordance with the

currently approved protocol and any other study agreements, ICH GCP, and all applicable regulatory requirements.

- Records and documents, including signed ICF, pertaining to the conduct of this study must be retained by the investigator for 25 years from the issue of the final Clinical Study Report(CSR) or equivalent summary unless local regulations or institutional policies require a longer retention period. No records may be destroyed during the retention period without the written approval of the sponsor. No records may be transferred to another location or party without written notification to the sponsor.

Source Documents

- Source documents provide evidence for the existence of the participant and substantiate the integrity of the data collected. Source documents are filed at the investigator's site.
- Data reported on the CRF or entered in the eCRF that are transcribed from source documents must be consistent with the source documents or the discrepancies must be explained. The investigator may need to request previous medical records or transfer records, depending on the study. Also, current medical records must be available.
- Definition of what constitutes source data can be found in the SRM.

Study and Site Closure

GSK or its designee reserves the right to close the study site or terminate the study at any time for any reason at the sole discretion of GSK. Study sites will be closed upon study completion. A study site is considered closed when all required documents and study supplies have been collected and a study-site closure visit has been performed.

The investigator may initiate study-site closure at any time, provided there is reasonable cause and sufficient notice is given in advance of the intended termination.

Reasons for the early closure of a study site by the sponsor or investigator may include but are not limited to:

- Failure of the investigator to comply with the protocol, the requirements of the IRB/IEC or local health authorities, the sponsor's procedures, or GCP guidelines
- Inadequate recruitment of participants by the investigator
- Discontinuation of further study treatment development

12.4. Appendix 4: Adverse Events: Definitions and Procedures for Recording, Evaluating, Follow-up, and Reporting

Definition of AE

AE Definition

- An AE is any untoward medical occurrence in a clinical study participant, temporally associated with the use of a study treatment, whether or not considered related to the study treatment.
- NOTE: An AE can therefore be any unfavorable and unintended sign (including an abnormal laboratory finding), symptom, or disease (new or exacerbated) temporally associated with the use of a study treatment.

Events Meeting the AE Definition

- Any abnormal laboratory test results (hematology or clinical chemistry) or other safety assessments (e.g., ECG, radiological scans, vital signs measurements), including those that worsen from baseline, considered clinically significant in the medical and scientific judgment of the investigator (i.e., not related to progression of underlying disease).
- Exacerbation of a chronic or intermittent pre-existing condition including either an increase in frequency and/or intensity of the condition.
- New conditions detected or diagnosed after study treatment administration even though it may have been present before the start of the study.
- Signs, symptoms, or the clinical sequelae of a suspected drug-drug interaction.
- Signs, symptoms, or the clinical sequelae of a suspected overdose of either study treatment or a concomitant medication. Overdose per se will not be reported as an AE/SAE unless it is an intentional overdose taken with possible suicidal/self-harming intent. Such overdoses should be reported regardless of sequelae.
- "Lack of efficacy" or "failure of expected pharmacological action" per se will not be reported as an AE or SAE. Such instances will be captured in the efficacy assessments. However, the signs, symptoms, and/or clinical sequelae resulting from lack of efficacy will be reported as AE or SAE if they fulfill the definition of an AE or SAE.
